2. STUDY OBJECTIVES

2.1 Primary Objective

The primary objective of this study is to evaluate the efficacy of rivoceranib administered with best supportive care (BSC) in the target population in terms of improving overall survival compared with that of placebo administered with best supportive care (BSC).

2.2 Secondary Objective

The secondary objectives of this study are as follows:

- To evaluate progression-free survival (PFS)
- To evaluate objective response rate (ORR)
- To evaluate disease control rate (DCR)
- To evaluate EORTC QLQ-C30 and EORTC QLQ-STO22
- To evaluate EQ-5D-5L
- To explore pharmacodynamic markers:
Vascular Endothelial Growth Factor (VEGF), sVEGFR-1, sVEGFR2, and sVEGFR3
- To evaluate pharmacokinetics

Moreover, the safety of rivoceranib will be evaluated and safety measures are as follows:

- Adverse events, laboratory tests, vital signs, physical examination, 12-lead ECG, and ECOG performance status

3. INVESTIGATIONAL PLAN

3.1 Overall Study Design and Plan

This is a prospective, randomized, double-blinded, placebo-controlled, multinational, multicenter, parallel-group, phase III study to evaluate the efficacy and safety of Rivoceranib plus Best Supportive Care (BSC)

compared to Placebo plus BSC in subjects with advanced or metastatic gastric cancer who failed two or \geq three prior treatment regimens.

After informed consent and screening procedures, eligible subjects will be randomized in a 2:1 ratio to Rivoceranib or Placebo group. All subjects will receive best supportive care (BSC). The randomization will be stratified by the following factors: Geographic region (Asia vs. North America/Europe), Disease measurability (measurable vs. nonmeasurable), Prior ramucirumab treatment (Yes vs. No), and Treatment therapy line (3rd vs. \geq 4th).

Randomized subjects will receive either the test product Rivoceranib (freebase) at 700 mg/day plus BSC or Placebo plus BSC and will be evaluated at regular site visits, which will be made every 2 weeks till the death of the subject or discontinuation of the study treatment due to disease progression, intolerable toxicity or subject's withdrawal of consent. If treatment related toxicity is detected, two steps of dose reductions (600 mg, 400 mg for Rivoceranib) are allowed during the entire study period according to the dose adjustment plan.

Tumor response and progression will be assessed every other cycle (8 weeks interval) by a local imaging facility. Subject treatment decisions will be made based on local imaging results and investigator opinion which will be entered into the case report forms. Scans will be obtained at baseline and throughout the study and will be analysed post-study by a central imaging analysis facility. Centrally imaging results will determine the subjects best tumor response and time of progression according to RECIST 1.1.

Post-treatment follow-up visit will be made at 4 weeks after the end of treatment (EOT) and then survival follow-ups will follow at 8-week intervals till the death of the subject or closure of the study.

The study data will be analysed when the required number of events (approximately 325 deaths) are observed. This is projected to occur approximately 9 months after the last subject is randomized. All subjects will be treated and/or followed after randomization until the study data analysis is performed, and then they will be monitored for survival status until death.

Subjects on treatment after analysis will be provided an option to enroll in a treatment maintenance (the Extension period) protocol if approved by country and local regulatory authorities.

3.2 Study Duration

Total study duration was designed to be approximately 18 months: 9 months of recruitment period + 9 months of treatment period. The study recruitment period extended to 21 months thus total study duration became 30 months in Protocol version 4.1 and in subsequent Protocol version 5.0. The extension period may continue beyond 30 months. The study data will be analysed when the required number of events (approximately 325 deaths) are observed. This is projected to occur approximately 9 months after the last subject is randomized. All subjects will be treated and/or followed after randomization until the study data analysis is performed, and then they will be monitored for survival status until death. Patients continuing to benefit from rivoceranib treatment, after final analysis and subsequent unblinding, will be given an option to consent to continue treatment with rivoceranib. Placebo patients will stop taking the placebo and will be monitored for survival status until death.

3.3 Administration of Investigational Product

Investigational products will be administered orally once a day, approximately 1 hour after breakfast. It is recommended that the administration time should be consistent throughout the study period (that is, the administration interval should be approximately 24 hours). The investigational product should not be taken until during the clinic visit of Day 1 of each cycle.

Subjects should take 3 tablets of 200 mg and 1 tablet of 100 mg in strength at a time. If the dose is reduced to 600 mg, 3 tablets of 200 mg in strength should be taken. If the dose is reduced further to 400 mg, only 2 tablets of 200 mg in strength should be taken at a time. If the subject vomits after swallowing the IP, the dose will not be replaced and there will be no replacement of a missed dose of IP.

3.4 Randomization

Subjects will be randomized in a 2:1 ratio to the Rivoceranib group or the Placebo group, and the randomization will be stratified according to the following factors.

1. Geographic region (Asia pacific vs. North America/Europe)
2. Disease measurability (Measurable vs. Non-measurable)
3. Prior ramucirumab treatment (Yes vs. No)
4. Treatment therapy line (3rd vs. ≥ 4th)

For each subject who has provided written consent and whose eligibility is confirmed, a registration number will be assigned by the Interactive Web Response System (IWRS), and the subject will be enrolled in the study (enrollment). Detailed procedures for IWRS use will be specified in a separate document.

3.5 Japan Specific Safety Run-in

The AM104 ethnic bridging study determined that there is no statistically significant difference in Japanese ethnic population pharmacokinetics as compared to Chinese and/or Caucasian that would make it unsafe to proceed at the study starting dose. The AM104 study evaluated the pharmacokinetics of a single dose of 201 mg of Rivoceranib in 18 healthy volunteers of each of three specific ethnic populations; Japanese, Chinese and Caucasian. Initiation of enrollment in Japan included a safety run-in approach to further confirm the safety of the study starting dose in this ethnic population.

Initially, in Japan, only 6 subjects were enrolled and assigned either Rivoceranib or Placebo to investigate the safety at the same starting dose and with the same randomization/enrollment criteria as all other study subjects. The treatment assignments were not known to any study personnel with the following exceptions. During the observation period, an appropriately unblinded and separate study personnel in the study team who would perform no other study activity or duties that would jeopardize the integrity of the study, determined whether at least 3 of the first 6 subjects were assigned to Rivoceranib treatment. These specific subjects were hospitalized and monitored during the 14 days of DLT evaluation period including performing the following evaluations once on either study day 7, 8 or 9 that was not noted in the standard study schedule,

- Physical examination
- Measurement of vital signs including weight

- Assessment of ECOG performance score
- Assessment of adverse event
- Collection of concomitant medication information
- Hematology, blood chemistry, coagulation test and urinalysis

If at least 3 were assigned Rivoceranib treatment, the Rivoceranib treated subjects would be observed for a minimum of 14 days of therapy. If less than 3 subjects were randomized to Rivoceranib treatment, 3 more subjects (bringing the total to 9 subjects) could have been enrolled immediately to ensure that the DLT evaluation in Japan subjects was performed on at least 3 Rivoceranib treated subjects.

If no DLT occurred during the DLT evaluation period (at least 0/3 rivoceranib treated subjects), the study could proceed in Japan with further enrollment per protocol and the IDMC and PMDA would be notified.

If there was only 1 DLT during the DLT evaluation period (at least 1/3), another 3 subjects could have been enrolled to ensure that at least 6 Rivoceranib subjects were observed for the 14 day DLT evaluation period.

If there remained only 1 DLT during the DLT evaluation period after at least 6 Rivoceranib treated subjects were observed (at most 1/6 Rivoceranib treated subjects), the study could proceed in Japan with further enrollment per protocol and the IDMC and PMDA would be notified.

If there were 2 DLT events in the 14 day DLT evaluation period (either at most 2/3 or at least 2/6 Rivoceranib treated subjects), then the subject data (AE, SAE, DLT, etc) in EDC with randomization information would be sent to the independent contract research organization for interim analyses (AXIO Research, LLC). AXIO would merge the subject information with the randomization information for presentation to the IDMC. AXIO would schedule a teleconference to review the information with the IDMC, which would discuss recommendation regarding whether discontinue or continue enrollment with or without study design modifications. Such a study design modification could be but not limited to:

- Dose modification
- Extended safety run-in
- Request for additional safety monitoring

Then AXIO would transfer the IDMC's recommendation to LSKB and LSKG. The enrollment in Japan would temporarily stop until sponsor's decision to discontinue or continue enrollment with or without modifications after consultation with PMDA.

The notification of the outcome of the Japan Safety Run-in would also be given to each site. In addition, if a DLT occurred, a notification would be made in a timely manner to all investigators that had subjects being treated on study.

For the purposes of the Japanese safety run-in, a DLT is defined as any of the following events assessed by the Investigator as probably or possibly related to Rivoceranib that occurs during or after the initial dose on Day 1 through Day 14.

1. CTCAE Grade 4 event
2. Grade 3 febrile neutropenia (<1,000 neutrophils/mm³)
3. Grade 3 anemia and thrombocytopenia with duration > 7 days
4. Grade 3 non-hematologic toxicity including Grade 3 nausea, vomiting and diarrhea that

- continues despite optimal medical management
5. Anemia or thrombocytopenia that requires transfusion
 6. When the study treatment was withheld based on the protocol 4.4 dose adjustment plan more than three day

Of note, the first 6 subjects enrolled in Japan were evaluable, were confirmed that at least 3 were administered rivoceranib and no DLT was observed in any of these subjects.

3.6 Study Scheme

Overview of study design is summarized in [Figure 1](#).

[figure not shown]

Figure 1. Study Scheme

- 1) Post-treatment follow-up will be done at 4 weeks (\pm 7 days) after the end of treatment (EOT).
- 2) Survival follow-up will be done at 8 weeks (\pm 7 days) interval after the Post-treatment follow-up visit. Survival follow-ups will continue until the death of the subject or till the study closure.

3.7 Determination of the Sample Size

A large black rectangular redaction box covers the majority of the page content, positioned in the upper half. Below this, there are several horizontal black bars of varying lengths, some with small black squares at their start. A vertical dashed line is located on the left side, intersecting the horizontal bars. The bottom portion of the page is also blacked out.

4. ANALYSIS SETS

4.1 Intention-To Treat Set

ITT set consists of data from all subjects who are randomized into the study. In the ITT set, subjects will be included in the group to which they were randomized. The ITT set will be used for the primary efficacy analyses.

4.2 Safety Set

Safety set consists of data from all subjects in the ITT population who received at least one dose of Rivoceranib or placebo. In the Safety set, subjects will be included in the group based on the treatment that was received. Safety data will be analyzed by safety set.

4.3 Full Analysis Set

FAS consists of data from subjects included in ITT Set who received at least one dose of Rivoceranib or placebo. The FAS will be used for supportive efficacy analyses.

4.4 Per-Protocol Set

PPS consists of data from subjects included in FAS who completed the study per protocol without major violation such as inclusion/exclusion criteria violation and use of prohibited concomitant medication during the study. The PPS will be used for supportive efficacy analyses. Whether each subject is included in the PPS will be decided in a blinded meeting based on the protocol deviations and violations before data base lock.

5. STUDY VARIABLES AND DEFINITIONS

5.1 Efficacy Variables

Based on the definition of target and non-target lesion, response of target lesions and response of non-target lesion are defined in [Table 1](#) and [Table 2](#) in the RECIST1.1. Centrally imaging results will determine the subjects best tumor response and time of progression according to RECIST 1.1.

Table 1. Response Criteria of Target Lesions

Response of Target Lesions	Definition
Complete response (CR)	The disappearance of all target lesions and reduction in short axis of any nodal target lesions to < 10 mm
Partial Response (PR)	At least a 30% decrease in the sum of the longest diameters of the target lesions, taking as a reference the baseline sum diameters
Stable Disease (SD)	Neither sufficient shrinkage to qualify for PR nor sufficient increase to qualify for PD, taking as a reference the smallest sum diameters while on study.

Response of Target Lesions	Definition
Progressive Disease (PD)	At least a 20% increase in the sum of the diameters of the target lesions, taking as a reference the smallest sum on study (this includes the baseline sum if that is the smallest on study). In addition to the relative increase of 20%, the sum must also demonstrate an absolute increase of at least 5 mm. (Note: the appearance of one or more new lesions is also considered progression).

Table 2. Response Criteria of Non-Target Lesions

Response of Non-Target Lesions	Definition
CR	Disappearance of all non-target lesions and normalisation of tumour marker level. All lymph nodes must be non-pathological in size (<10mm short axis).
non-CR/non-PD	Persistence of one or more non-target lesion(s) and/or maintenance of tumor marker level above the normal upper limits
PD	Unequivocal progression of existing non-target lesions (Note: the appearance of one or more new lesions is also considered progression).

With the tumor response of target, non-target and new lesion, overall response is defined in [Table 3](#).

Table 3. Time Point Response (subjects with target and non-target lesions)

Target Lesions	Non-Target Lesions	New Lesions	Overall Response
CR	CR	No	CR
CR	Non-CR/non-PD	No	PR
CR	Not evaluated	No	PR
PR	Non-PD or not evaluated	No	PR
SD	Non-PD or not evaluated	No	SD
Not evaluated	Non-PD	No	Inevaluable (NE)
PD	Any response	Yes or No	PD
Any response	PD	Yes or No	PD
Any response	Any response	Yes	PD

With the tumor response of non-target and new lesion, overall response is defined in [Table 4](#)

Table 4. Time Point Response (subjects with non-target lesions only)

Non-Target Lesions	New Lesions	Overall Response
CR	No	CR
Non-CR/non-PD	No	Non-CR/non-PD
Not evaluated	No	Inevaluable (NE)
Unequivocal PD	Yes or No	PD
Any response	Yes	PD

The best overall response without confirmation of complete or partial response is defined as the best response across all time points. When there are more than one response, it will be selected as the best overall response according to the order of CR > PR > SD > NON-CR / NON-PD > PD > NE. The minimum duration for SD to decide best response is 6 weeks.

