### **6.3. Treatment continuation after disease progression**

Patients who will be treated beyond disease progression must review and sign a supplemental informed consent form before continuing on study drug. In addition, the following activity must be performed and the investigator must provide documentation of their opinion with supporting laboratory evaluation data that:

- The patient demonstrates investigator-assessed potential for clinical benefit and does not have rapid disease progression.
- It is safe to continue study drug and the patient, by evidence of signing consent, is tolerant of any continuing adverse events.
- ECOG performance status of 0 or 1 or stable ECOG performance status of 2 with no signs of rapid deterioration (ECOG status of 2 for past three months or more where the investigator feels that the deterioration of ECOG performance status from baseline at study entry is not indicative of potential to have serious adverse events within at least 30 days from beginning of continuation study treatment).
- The patient has a life expectancy of more than 30 days.
- Treatment beyond progression will not delay an imminent intervention to prevent serious complications of disease progression (e.g., CNS metastases).
- A radiographic assessment/scan should be performed approximately 8 weeks ( $\pm 7$  days), or earlier if the patient is exhibiting symptoms that may indicate continued progression, after initial Investigator-assessed progression to determine whether there has been a decrease in the tumor size or continued progressive disease. The assessment of clinical benefit should be balanced by clinical judgment as to whether the patient is clinically deteriorating and unlikely to receive any benefit from continued treatment with study therapy.

For the patients who continue receive study therapy beyond progression, further progression is defined as an additional 15% increase in tumor burden from time of initial progression. This includes an increase in the sum of diameters of all target lesions and/or the diameters of new measurable lesions compared to the time of initial progression or

rapid deterioration in the performance status. Study treatment should be discontinued permanently upon documentation of further progression.

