### 8.2.2. Secondary Efficacy Endpoints

- Progression Free Survival (PFS): Time from randomization to either radiological progression or death. Subjects alive and free of progression at the end of study (EOS) are censored.
- Objective Response Rate (ORR): Percentage of subjects with a Best Overall Response of Complete Response (CR) or Partial Response (PR).
- Disease Control Rate (DCR): Proportion of subjects with a Best Overall Response of complete or partial response, or stable disease.
- Global health status/quality of life score according to European Organization for Research and Treatment of Cancer Quality of Life Questionnaire-Core 30 (EORTC QLQ-C30) and EORTC QLQ-STO22
- Each dimension response according to EuroQol 5-Dimension 5-Level (EQ-5D-5L) Questionnaire

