**Table 4. Best Overall Response When Confirmation Of CR And PR Required**

Overall Response First Time Point	Overall Response Subsequent Time Point	BEST Overall Response
CR	CR	CR
CR	PR	SD, PD or PR a
CR	SD	SD provided minimum criteria for SD duration met, otherwise, PD
CR	PD	SD provided minimum criteria for SD duration met, otherwise, PD
CR	NE	SD provided minimum criteria for SD duration met, otherwise, NE
PR	CR	PR
PR	PR	PR
PR	SD	SD
PR	PD	SD provided minimum criteria for SD duration met, otherwise, PD
PR	NE	SD provided minimum criteria for SD duration met, otherwise NE
NE	NE	NE

a If a CR is truly met at the first time point, then any disease seen at a subsequent time point, even disease meeting PR criteria relative to baseline, makes the disease PD at that point (since disease must have reappeared after CR). The best response would depend on whether minimum duration for SD was met. However, sometimes 'CR' may be claimed when subsequent scans suggest small lesions were likely still present and in fact the patient had PR, not CR at the first time point. Under these circumstances, the original CR should be changed to PR and the best response is PR.

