5.1.2 Efficacy Variables Secondary Endpoints

Centrally imaging results will determine the subject's best tumor response and time of progression according to RECIST 1.1. for the following endpoints. In addition, supportive tumor response and progression will be analyzed based on investigator assessment.

- Progression Free Survival (PFS): Time from randomization to either documented radiological progression (PD) or death. Subjects alive and free of progression are censored at the last tumor assessment date when alive and free of progression were known. And if there is no baseline tumor assessment data for subjects, the subjects are censored at the date of randomization.
- Objective Response Rate (ORR): Proportion of subjects with a Best Overall Response of Complete Response (CR) or Partial Response (PR).
- Disease Control Rate (DCR): Proportion of subjects with a Best Overall Response of complete response (CR) or partial response (PR), or stable disease (SD).

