7.5 Efficacy Analysis

7.5.1 Multiple Comparison Procedure on Primary and Key Secondary Endpoints

To control the family-wise error rate (FWER) on testing multiple hypotheses of interest, the fixed sequence closed testing procedure will be used. In this fixed sequence procedure, each hypothesis will be sequentially tested with two-sided 5% level only if higher level hypothesis is rejected. For this fixed sequential testing, the primary and key secondary efficacy endpoints will be tested using the ITT set. Specifically,

1. Test OS with two-sided 5% level
2. If OS is significant, test PFS (based on central review) with two-sided 5% level
3. If OS and PFS are significant, test ORR (based on central review) with two-sided 5% level

If a prior test is not statistically significant, then the subsequent analyses will be exploratory rather than confirmatory.

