7.5.3 Key Secondary Efficacy Analysis

The key secondary efficacy endpoints (PFS, ORR) will be analyzed using ITT, FAS and PPS. The key secondary efficacy analyses will be conducted using the ITT set.

- Progression Free Survival (PFS): Time from randomization to either documented radiological progression (determined by the central imaging analysis facility) or death from any cause. Subjects alive and free of progression are censored at the last tumor assessment date when alive and free of progression were known.
- Objective Response Rate (ORR): Percentage of subjects with a Best Overall Response (determined by the central imaging analysis facility) of Complete Response (CR) or Partial Response (PR).

PFS will be analyzed using the same statistical methods that are used in the primary efficacy analysis of OS.

ORR will be analyzed using the Cochran-Mantel-Haenszel test stratified by the randomization stratification factors Geographic region (Asia vs. North America/Europe), Prior ramucirumab treatment (Yes vs. No), and Treatment therapy line (3rd vs. ≥ 4th). For the ORR, the frequency and percentage (with 95% CI) of subjects will also be provided.

Data will be summarized in the following tables and figures.

-Table. Progression Free Survival [Independent Central Review] – ITT

-Table. Progression Free Survival [Independent Central Review] – FAS

-Table. Progression Free Survival [Independent Central Review] – PPS

-Figure. Kaplan Meier Plot for Progression Free Survival [Independent Central Review] - ITT

-Figure. Kaplan Meier Plot for Progression Free Survival [Independent Central Review] - FAS

-Figure. Kaplan Meier Plot for Progression Free Survival [Independent Central Review] – PPS

-Table. Objective Response Rate [Independent Central Review] – ITT

-Table. Objective Response Rate [Independent Central Review] – FAS

-Table. Objective Response Rate [Independent Central Review] – PPS

-Table. Progression Free Survival - [Investigator Review] – ITT

-Table. Progression Free Survival - [Investigator Review] – FAS

-Table. Progression Free Survival - [Investigator Review] – PPS

-Table. Objective Response Rate - [Investigator Review] – ITT

-Table. Objective Response Rate - [Investigator Review] – FAS

-Table. Objective Response Rate - [Investigator Review] – PPS

- List. Time to Event Parameters by Subjects – ITT Set

- List. Objective Response by Subject – ITT Set

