13. CHANGE FROM PROTOCOL

Protocol v5.0 Location(s)	SAP Location(s)	Protocol v5.0 Language	SAP Language Changed from Protocol v5.0	Reason of Change
Section 8.1.1 p.73	Section 3.7.1 p.15	"Where HR (hazard ratio) is the ratio of median overall survival of Placebo and Rivoceranib* group."	"where HR (hazard ratio) is the ratio of median overall survival of denotes the hazard ratio for Rivoceranib group relative to Placebo group. "	Clarify language in the protocol.
Section 8.1.3 p.74	Section 3.7.3 p.16	"325 events (413 subjects) are needed."	" a total of 325 events (413 subjects) are needed to provide approximately 80% power for Overall Survival. "	Clarify language in the protocol.
Section 8.3.2 p.75	Section 4.1 Section 4.2 Section 4.3 Section 4.4 p.17	"ITT set consists of data from all subjects who are randomized." "The analysis for primary endpoint, OS and the secondary endpoints of PFS and ORR will be conducted in the ITT set." "Safety set consists of data from all subjects who received at least one dose of Rivoceranib or placebo." "The FAS will be used for all efficacy analyses." "The PPS will be used for all efficacy analyses."	"ITT set consists of data from all subjects who are randomized into the study. " " The analysis The ITT set will be used for the primary efficacy analyses endpoint, OS and the secondary endpoints of PFS and ORR will be conducted in the ITT set. " "Safety set consists of data from all subjects in the ITT population who received at least one dose of Rivoceranib or placebo." "The FAS will be used for all supportive efficacy analyses." "The PPS will be used for all supportive efficacy analyses."	Clarification that ITT set will be used for the primary efficacy analyses, and FAS and PPS will be used for supportive efficacy analyses.

Protocol v5.0 Location(s)	SAP Location(s)	Protocol v5.0 Language	SAP Language Changed from Protocol v5.0	Reason of Change
Appendix 2: Table 3 p.91	Section 5.1 Table 4 Table 5 p.18	Table title: Time Point Response	Table title: Time Point Response (subjects with target and non-target lesion) Added table 5: Time Point Response (subjects with non-target lesion only)	Clarified on the original table and added a table to define response for subjects with non-target lesion only.

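### SAP 5.1 sets no end to the period over which best overall response is taken, so a response read after central progression would count in the confirmatory ORR

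*SAP*

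**What the plan says.** - **SAP 5.1, the only best-overall-response rule in the SAP:** "The best overall response without confirmation of complete or partial response is defined as the best response across all time points". Where a subject has several responses, the order is CR, PR, SD, non-CR/non-PD, PD, NE, with a six-week minimum for SD. No last eligible assessment is named.
- **SAP 5.1.2:** "Centrally imaging results will determine the subject's best tumor response and time of progression according to RECIST 1.1". PFS, ORR and DCR all use these central reads.
- **SAP 7.5.1:** ORR is the third step of the fixed sequence: "If OS and PFS are significant, test ORR (based on central review) with two-sided 5% level".
- **Protocol 6.3:** study drug may continue after progression: "Patients who will be treated beyond disease progression must review and sign a supplemental informed consent form before continuing on study drug". A further scan is due about 8 weeks after investigator-assessed progression.
- **Protocol 3.1:** local imaging and investigator opinion drive treatment decisions, and the central facility reads the scans after the study.
- **Protocol Appendix 2:** the one best-response table, Table 4, is headed "Best Overall Response When Confirmation Of CR And PR Required". The ORR definitions in protocol 8.2.2 and 8.3.5 do not say whether confirmation applies.
- **SAP section 13:** for the Appendix 2 response tables it lists only the change to Table 3 (the SAP "added a table to define response for subjects with non-target lesion only"). It has no entry for Table 4.

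**The concern.** PFS stops at the first centrally read progression, but best overall response does not stop anywhere. Because PR outranks PD, one later PR overrides an earlier PD for ORR while the PFS event stands. Two adjacent confirmatory endpoints, built on the same central reads, would then describe the same subject in opposite ways. Scans after central progression can arise in two ways: from subjects treated beyond progression, and from subjects whose central progression comes before the local call.

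What is at stake is the third confirmatory test. Few responders are expected, so a handful of such subjects could matter. The same definition also feeds DCR, which is not confirmatory.

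**Working it through.** **1. The rule applied to one sequence.** Take illustrative central reads at the planned 8-week interval, with no new lesions: SD at week 8, PD at week 16 (target sum at least 20% and 5 mm above its smallest value), PR at week 24 (at least 30% below baseline).

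| Endpoint | SAP as written | With a cut at first central PD |
|---|---|---|
| PFS | event at week 16 | event at week 16 |
| Best overall response | PR | SD |
| ORR | responder | non-responder |

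**2. Inputs for the size.** The readable text gives no expected rate, power or responder count for ORR, so there is no ORR figure to reproduce. The plan's OS figure does reproduce: with HR 0.72, 2:1 allocation, two-sided 5% and 80% power, the Schoenfeld formula gives 328 events against 325 stated, and 325 events give 79.7% power. This does not bear on ORR. The inputs used are:
- 459 subjects at 2:1 (protocol 3.1), so 306 on drug and 153 on placebo;
- earlier phase III ORR of 2.84% vs 0.00% (protocol 1.2), which is 0.0284 × 176 = 5.0 responders in that trial;
- phase II (protocol 1.2): 3 PRs in the once-daily arm, with 144 patients in three groups.

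**3. Formula.** For a single-stratum CMH test, with *a* responders on drug and *T* in total:

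z = (a − 2T/3) / √[T × (2/9) × (459 − T)/458]

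For 9 vs 0: z = (9 − 6) / √(9 × 0.2222 × 450/458) = 3/1.402 = 2.14, so p = 0.032.

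**4. At the phase III rate.** 306 × 0.0284 = 8.7 expected responders on drug and none on placebo.

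| Drug vs placebo | p |
|---|---|
| 9 vs 0 | 0.032 |
| 8 vs 0 | 0.044 |
| 7 vs 0 | 0.060 |
| 9 vs 1 | 0.114 |
| 12 vs 1 | 0.047 |

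If two of nine drug-arm responses arise only after progression, the cut moves 9 vs 0 to 7 vs 0. One such response on placebo moves 9 vs 0 to 9 vs 1. Removing a single drug-arm response from nine leaves 8 vs 0, which is still significant. The SAP stratifies on three factors, giving up to 8 strata. A simulated CMH with assumed stratum sizes gave median p-values of 0.033, 0.044 and 0.060 for 9, 8 and 7 vs 0, so stratification does not alter the picture.

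**5. At the phase II once-daily rate.** Group sizes are not given. Assuming 144/3 = 48 per group, 3/48 = 6.25%, and 306 × 0.0625 = 19.1 responders.

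| Drug vs placebo | p |
|---|---|
| 19 vs 0 | 0.002 |
| 17 vs 0 | 0.003 |
| 19 vs 1 | 0.006 |
| 17 vs 2 | 0.031 |

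If the group held between 40 and 56 patients, the expected count would run from 306 × 3/40 = 23 down to 306 × 3/56 = 16. Even 14 vs 1 gives p = 0.026. At these rates one or two subjects do not change the result.

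**The case against.** **Scanning is already partly bounded.** Protocol 5.2.1 continues imaging after withdrawal for reasons other than progression only until progression or other tumour treatment. Protocol 4.7.1 bars other anti-cancer therapy during treatment. This stands: a stop at new therapy would change little. It does not cover the groups that matter here, namely subjects treated beyond progression and subjects whose central progression precedes the local call.

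**A PR after PD is hard to reach.** It needs a 30% fall from baseline, and any time point with a new lesion is PD whatever the other lesions show. Protocol 6.3 also restricts who continues. This stands too, and is why the cases are probably few. The documents give no basis for a count.

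**RECIST 1.1 or the imaging manual may supply the cut.** They may, but the manual is not among the documents. The one operative sentence in the SAP sets no limit, and a general reference to RECIST does not override it.

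**A reader might infer that the SAP reverses a protocol requirement for confirmed response.** The documents do not support that. The heading of Table 4 is conditional, and no protocol ORR definition requires confirmation. An unconfirmed rule is a legitimate choice in a double-blind randomised trial. Its only defect is that section 13 does not set it against Table 4.

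**A reader might also infer that the rule favours the drug, or that it will decide the ORR test.** Neither is shown. The same rule applies to both blinded arms, and the 9 vs 1 case shows it can cost significance. The fragile result rests on one earlier rate, from about five responders whose confirmation status is not stated.

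**Conclusion.** The point holds as a gap in a definition. As written, SAP 5.1 lets one subject be both a PFS progression event and a later responder in the confirmatory ORR.

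Its size is conditional. At about 9 vs 0 responders, two drug-arm cases or one placebo case would cross the 5% line. At about 19 vs 0 they would not. These figures assume full enrolment of 459, response rates carried over from earlier trials and, for phase II, equal groups. The number of post-progression responses is unknown and probably small.

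ORR is tested confirmatorily only if OS and PFS both succeed; the OS analysis and the sample size are untouched. The correction should still be made before unblinding, because a cut chosen once responder counts are known would look selected by result.

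**What to change.** 1. **SAP 5.1:** limit best overall response to assessments from randomisation up to and including the first centrally read progression, or up to the start of new anti-cancer therapy if that is earlier.
2. **SAP 5.1 and section 13:** keep the unconfirmed rule for the primary ORR if that is intended. Say so plainly, and add a row to section 13 declaring it against protocol Appendix 2 Table 4.
3. **SAP 7.5.3:** report confirmed ORR as a sensitivity analysis.

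The cost is two sentences, one row and one extra table. The downside is that ORR may come out slightly lower. Nothing in treatment or in the scan schedule changes.
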